1 PROTOCOL SUMMARY

1.1 SYNOPSIS

Title:	Connectomic Analysis in Dementia with Lewy Bodies: A Potential Diagnostic Imaging Biomarker
IRB Number:	A#_21-037_____
Study Description:	This is a cross-sectional study in patients with Lewy Body Dementia (DLB) with two comparison groups (AD and cognitively normal controls) drawn from a publicly available database called ADNI-2/3. We intend to study dysfunctional large scale brain networks (LSBNs) in DLB by comparing resting state functional MRI (rs-fMRI) imaging data. We propose using a novel cloud-based automated imaging software processing program that identifies abnormal brain networks or connectomes using rs-fMRI and data from the Human Connectome Project (HCP).
Specific Aims:	Specific Aim #1: Evaluate the role of rs-fMRI and connectomic analysis as a diagnostic imaging biomarker for LSBN deterioration in DLB by comparing a clinic population of DLB patients with pre-existing data from an ADNI 2/3 cohort of CN and MCI/mild AD subjects Specific Aim #2: Correlate cross-sectional dysfunction between LSBN parcellations with specific neuropsychological abnormalities in DLB patients
Outcomes:	Aim 1 Outcomes: Functional connectivity (FC) scores between pairs of LSBN parcellations. Aim 2 Outcomes: Functional connectivity (FC) scores between pairs of LSBN parcellations vs Neuropsychological test scores
Study Population:	Inclusions: 1) Age 40- 90 years, 2) Established DLB diagnosis (McKeith Criteria 2017), 3) MMSE>15 Exclusions: 1) Other forms of dementia including, but not limited to Alzheimer's dementia, frontotemporal dementia, vascular dementia, NPH, etc, 2) Inability to tolerate brain fMRI, 3) Risk of brain fMRI due to implants or metal. Sample Size: We plan to enroll 19 DLB patients. 38 AD and 38 CN age and sex-matched subjects will be selected from the ADNI-2/3 database.
Description of Sites/Facilities Enrolling Participants:	Participants will be enrolled at HealthPartners Neuroscience Center, located at [name].
Study Duration:	The duration of this study is 1.5 years.
Participant Duration:	Participants should take about 3 hours - total time for all the visits, that may be conducted within 6 weeks

2 INTRODUCTION

2.1 BACKGROUND & STUDY RATIONALE

Dementia with Lewy bodies (DLB) is a common neurodegenerative condition characterized by parkinsonism, hallucinations, and cognitive fluctuations. This disease represents the second most common cause of dementia, affecting 1.4 million individuals (www.lbda.org). In comparison to Alzheimer's disease (AD), DLB is a more rapid dementia that not only results in progressive cognitive decline, but also leads to a variety of non-cognitive symptoms that include motoric impairment, REM sleep behavioral disorder, psychosis, and autonomic dysfunction. Disease progression is predicated on the propagation of alpha-synuclein aggregates from peripheral nervous system locations such as the olfactory cortex and enteric nervous system to central nervous system structures that include the brainstem and temporal cortex, thus resulting in progressive deterioration of LSBNs (H Braak J Neurol 200).

Detection rates of DLB in clinical practice are suboptimal (Jones & O'brien, 2014). To facilitate the diagnosis of this relatively common dementia, revised criteria have been developed based on core clinical features, supportive clinical features, and indicative biomarkers (**table 1**) (McKeith et al., 2017). The diagnosis of probable DLB (greatest degree of certainty in the absence of confirmatory brain pathology) can be made when a patient has either **2 core clinical features or one clinical feature** accompanied by **one indicative biomarker**. In contrast to most other neurological diseases, the indicative biomarkers in DLB measure indirect effects of the disease: reduced dopamine transporter update on a DaT scan indicates parkinsonism, abnormal cardiac uptake on a ¹²³iodine-MIBG myocardial scintigraphy suggests autonomic dysfunction, and tonic contractions during REM sleep during polysomnography supports REM sleep behavioral disorder. Limitations of these tests include a lack of specificity for this diagnosis (findings can be seen in Parkinson's disease or multiple system atrophy), relatively higher costs, and lack of insurance coverage as in the case of the DaT scan.

Further complicating matters, there are no universal imaging tools that directly show the impact of DLB on the CNS. Structural brain MRI is relatively less helpful for diagnostic classification, described as a "supportive biomarker" meaning that it has a less critical role in determining diagnosis. MRI will support a DLB diagnosis when there is an absence of medial temporal lobe atrophy, commonly found in Alzheimer's disease. However, the sensitivity and specificity of this diagnostic test is suboptimal: a

Table 1: Criteria for Dementia with Lewy Bodies

Table 1 Revised^{1,2} criteria for the clinical diagnosis of probable and possible dementia with Lewy bodies (DLB)

Essential for a diagnosis of DLB is dementia, defined as a progressive cognitive decline of sufficient magnitude to interfere with normal social or occupational functions, or with usual daily activities. Prominent or persistent memory impairment may not necessarily occur in the early stages but is usually evident with progression. Deficits on tests of attention, executive function, and visuoperceptual ability may be especially prominent and occur early.

Core clinical features (The first 3 typically occur early and may persist throughout the course.)

Fluctuating cognition with pronounced variations in attention and alertness.
Recurrent visual hallucinations that are typically well formed and detailed.
REM sleep behavior disorder, which may precede cognitive decline.
One or more spontaneous cardinal features of parkinsonism: these are bradykinesia (defined as slowness of movement and decrement in amplitude or speed), rest tremor, or rigidity.

Supportive clinical features

Severe sensitivity to antipsychotic agents; postural instability; repeated falls; syncope or other transient episodes of unresponsiveness; severe autonomic dysfunction, e.g., constipation, orthostatic hypotension, urinary incontinence; hypersomnia; hyposmia; hallucinations in other modalities; systematized delusions; apathy, anxiety, and depression.

Indicative biomarkers

Reduced dopamine transporter uptake in basal ganglia demonstrated by SPECT or PET.
Abnormal (low uptake) ¹²³iodine-MIBG myocardial scintigraphy.
Polysomnographic confirmation of REM sleep without atonia.

Supportive biomarkers

Relative preservation of medial temporal lobe structures on CT/MRI scan.
Generalized low uptake on SPECT/PET perfusion/metabolism scan with reduced occipital activity ± the cingulate island sign on FDG-PET imaging.
Prominent posterior slow-wave activity on EEG with periodic fluctuations in the pre-alpha/theta range.

multisite study with autopsy confirmation showed that MRI was 64% sensitive and 68% specific for differentiating DLB from AD. Fluorodeoxyglucose positive emission tomography (FDG-PET), a functional biomarker that has been used to support a DLB diagnosis, shows occipital hypometabolism with relatively sparing of the posterior cingulate although these findings likewise lack sensitivity (83%) and specificity for DLB (80%) (Minoshima et al., 2001; Yamamoto et al., 2007).

The role of brain rs-fMRI, an imaging tool that maps interactions between brain regions during a resting state and produces a blood-oxygen-level-dependent signal, has been only preliminarily evaluated in patients with DLB. Currently, there is no defined pattern of LSBN deterioration in this condition. Certain investigations have failed to demonstrate characteristic differences between connectivity in DLB versus AD whereas others have demonstrated subtle difference (eg. increased precuneus-medial frontal connectivity (Galvin, Price, Yan, Morris, & Sheline, 2011). A study consisting of 18 DLB, 18 AD, and 15 CN subjects showed that posterior cingulate cortex connectivity was lower in AD than in DLB (Franciotti et al., 2013). Another study evaluated rs-fMRI functional connectivity in 15 DLB, 13, AD, and 40 controls, showing that functional connectivity was lower in DLB in the default mode, salience, and executive networks compared to the other groups (Lowther, O'Brien, Firbank, & Blamire, 2014) whereas a second study failed to show significant differences in LSBN connectivity between AD and DLB (Schumacher et al., 2018).

The core symptoms of DLB (hallucinations, cognitive fluctuations, parkinsonism, and REM sleep behavioral disorder) may offer clues to the specific LSBNs impacted by this disease. To our knowledge, few studies have evaluated the networks responsible for these symptoms and then attempted to leverage findings for diagnostic purposes. The locus coeruleus, a brainstem structure containing abundant noradrenergic neurons with ascending pathways throughout the central nervous system, has been found to exhibit cell loss in post-mortem analysis of DLB patients (Del Tredici & Braak, 2013) and may be responsible for the characteristic cognitive fluctuations (O'Dowd et al., 2019). fMRI studies have further shown that patients with disorders of consciousness exhibit compromise of those connections between the locus coeruleus, intralaminar nucleus of the thalamus, and nucleus basalis of Meynert (Edlow, Claassen, Schiff, & Greer, 2020). It has also been demonstrated that neuronal loss and Lewy bodies in the nucleus basalis of Meynert are correlated with the reduction of choline acetyltransferase levels in DLB (Lippa, Smith, & Perry, 1999). Thus, we suspect that the locus coeruleus and its ascending projections play a significant role in the arousal disturbances and cognitive fluctuations in DLB. Parkinsonism results from disruption of connections between the substantia nigra and basal ganglia structures (Young & Penney, 1984). Furthermore, findings of attention/executive dysfunction in DLB correlate with the basal ganglia, particularly the left caudate nucleus (Botzung, Philippi, Noblet, de Sousa, & Blanc, 2019). Finally, hallucinations in Lewy body are thought to involve dysfunction in a variety of brain areas. A systemic literature search of 56 neuroimaging studies in PD and DLB with visual hallucinations were reviewed—the main structural neuroimaging results showed grey matter loss in the frontal areas whereas functional investigations revealed parietal and temporal hypometabolism in PD with hallucinations (Pezzoli, Cagnin, Bandmann, & Venneri, 2017). Disrupted functional connectivity was also detected in the fronto-parietal regions through fMRI studies. One structure, the inferior longitudinal fasciculus (ILF), which connects the occipital lobe with the temporal lobe, has been found to be dysfunctional in DLB (Kantarci et al., 2010). We suspect that brain regions within this pathway may be compromised in DLB patients with visual hallucinations. Preliminary work from our group has shown from that area PH, a region located within the anterioinferior lateral occipital lobe and lateral to the occipitotemporal sulcus, is associated with visual hallucinations in schizophrenia and has white matter connections within the ILF. This area is a higher-level perception region of the visual system that acts as a hub of ventral stream input, integrating “place-specific” information, while showing little to no activity to objects or faces (Baker, Burks, Briggs, Milton,

et al., 2018). There are connections to other brain regions including area or hub FST, which is involved in integrating information related to detail, motion, and form. Thus, our study will focus on pairwise functional connectivity between the seven parcellations listed in **Table 2**.

Table 2. Parcellations of Interest for Each DLB Core Symptom and Associated LSBN		
DLB Core Symptom	Associated Large Scale Brain Network	Parcellations of Interest
Cognitive fluctuations	Ascending brainstem norepinephrine tracts	Locus coeruleus, basal nucleus of Meynert, intralaminar nucleus of thalamus (Edlow et al., 2020)
Visual hallucinations	Inferior longitudinal fasciculus	Areas PH and FST (Pezzoli et al., 2017)
Parkinsonism	Ascending brainstem dopamine tracts	Substantia nigra, caudate nucleus (Young & Penney, 1984)

One potential challenge for functional imaging to this point is that brain parcellations (or distinct brain partitions) have been based on outdated models such as the Broadmann map from the 19th century (Zilles, 2018). In 2009, the Human Connectome Project (HCP) began one of the most ambitious neuroscientific initiatives to map the brain (Fox, 2018; Glasser et al., 2016). This project identified 379 functional areas of the brain and discovered 97 new regions that had never been previously described. This data has provided neuroscientists for the first time in history the ability to view the brain not merely as a structural entity, but as an individualized network system.

Figure 1: Infinitome Program – Removed for CT.GoV version

Omniscient, a for-profit, Sydney, Australia-based company, created the cloud-based software Infinitome, a program that utilizes data from the HCP together with machine learning to analyze diffusion tensor and resting-state fMRI imaging data from remote sites (**Figure 1**). The foundation for this imaging tool is based upon the HCP atlas, which has also informed prior publications from our group, including the Connectomic Atlas of the Human Cerebrum (Baker, Burks, Briggs, Conner, et al., 2018). The Infinitome program creates a subject specific version of the Human Connectome Project Multimodal Parcellation (HCP-MMP1) atlas using diffusion tractography. Analytics are performed on both diffusion tensor imaging and rs-fMRI. Outlier detection using a tangent space connectivity matrix is performed by comparing results with a subset of 300 normal HCP subject fMRI samples to determine the range of normal correlations for each regions of interest in a LSBN. Abnormal connectivity is determined as a 3-sigma outlier for that correlation. The imaging protocol for rs-fMRI is limited to 15 minutes, enabling each study to be readily added on to structural MRI sequences. The program also provides automated image processing and analysis, thus simplifying the process of accessing imaging data and incorporating rs-fMRI into routine practice. By providing support for fMRI processing through a cloud-based server and incorporating normal control data from the HCP, this program addresses the challenges associated with the analysis and interpretation of rs-fMRI data. Thus, it has the potential to simplify the incorporation of rs-fMRI into clinical trials as a biomarker for neurodegeneration of vulnerable networks in DLB. Preliminary work has shown that connectomic analysis in AD subjects using this software is feasible and can detect functional anomalies involving regions of interest described by the HCP (Ren et al., 2020). Results from this proposal

will be applicable to both clinical practice and research where a diagnostic biomarker may impact either medical decision-making or enrollment into a clinical trial.

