3 OBJECTIVES AND ENDPOINTS

Aim 1: Evaluate the role of rs-fMRI and connectomic analysis as a biomarker of disease in DLB using data from an ADNI-2/3 population of MCI and mild AD subjects and a clinic population of DLB subjects

Functional connectivity (FC) scores between pairs of LSBN parcellations

- Primary pairs of interest (see background for justification of these choices):
 - Locus coeruleus v. Basal nucleus of Meynert
 - Locus coeruleus v. Intralaminar nucleus of thalamus
 - Basal nucleus of Meynert v. Intralaminar nucleus of thalamus
 - PH v. FST
 - Substantia nigra v. Caudate nucleus
- Exploratory pairs: Other 15 combinations of the pre-specified parcellations, other pairs of parcellations found to be anomalies by Infinitome program

Aim 2: Correlate cross-sectional and longitudinal dysfunction between LSBN parcellations with specific neuropsychological abnormalities in DLB Patients

Functional connectivity (FC) scores between pairs of LSBN parcellations (same primary pairs of interest as Aim 1).

Scores on neuropsychological tests: WMS-R Logical Memory Story A, Boston Naming Test Short, Category Fluency, WMS-R Digit Span Forward and Backward, ANART, RAVLT, Trails A/B, WMS-R Digit Symbol, Clock Drawing, NPI-Q, FAQ, ADAS-Cog 13

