8 STATISTICAL CONSIDERATIONS

8.1 STATISTICAL ANALYSIS PLAN

Preliminary data analysis: One-way ANOVA will be used to compare demographic and baseline clinical characteristics across groups. **no missing data expected, SAS, p-value

Aim 1 Analysis: For the between-group analysis of functional connectivity, general linear model multivariate analysis of variance will be used with FC values between pairs of LSBN parcellations as dependent variables and group (DLB, AD, and CN) as a factor variable. Bonferroni post hoc test will be used to correct for multiple comparisons. The primary pairs of interest (see **Table 4**) based on available literature (see background and **Table 2**) will be analyzed first. Other combinations of these seven parcellations will be analyzed secondarily. If additional, unexpected anomalies are present between groups, we will test them in an exploratory fashion to advance this novel field of study.

Aim 2 Analysis: Pearson correlation analyses will be performed between functional connectivity values and neuropsychological test scores to evaluate the relationship between connectivity strengths and the clinical phenotype of DLB. Similar to Aim 1, we will focus on pre-specified pairs of interest, but will explore others if they present themselves in the functional connectivity analysis.

Table 4: Data Variables
Population Descriptors: age, sex, race, ethnicity, education, measures of baseline cognition (e.g. MoCA)
Aim 1: Evaluate the role of rs-fMRI and connectomic analysis as a biomarker of disease in DLB using data from an ADNI-2/3 population of MCI and mild AD subjects and a clinic population of DLB subjects
Group variable: DLB, AD, or CN

Dependent variables: Functional connectivity (FC) scores between pairs of LSBN parcellations
 
 • Primary pairs of interest (see background for justification of these choices): 
 ○ Locus coeruleus v. Basal nucleus of Meynert ○ Locus coeruleus v. Intralaminar nucleus of thalamus ○ Basal nucleus of Meynert v. Intralaminar nucleus of thalamus ○ PH v. FST ○ Substantia nigra v. Caudate nucleus • Exploratory pairs: Other 15 combinations of the pre-specified parcellations, other pairs of parcellations found to be anomalies by Infinitome program
Aim 2: Correlate cross-sectional dysfunction between LSBN parcellations with specific neuropsychological abnormalities in DLB Patients

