Functional connectivity (FC) scores between pairs of LSBN parcellations (same primary pairs of interest as Aim 1).
Scores on neuropsychological tests: WMS-R Logical Memory Story A, Boston Naming Test Short, Category Fluency, WMS-R Digit Span Forward and Backward, ANART, RAVLT, Trails A/B, WMS-R Digit Symbol, Clock Drawing, NPI-Q, FAQ, ADAS-Cog 13

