06 FEB 2024

Aim 1

Our primary aim was to evaluate the role of rs-fMRI and connectomic analysis as a diagnostic imaging biomarker of disease for LSBN deterioration in DLB by comparing a clinical population of DLB patients with the ADNI 2/3 cohort of CN and AD/CI subjects. Specifically, we compared FC scores of prespecified parcellation pairs between the three groups using a one-way ANOVA. Eight parcellation pairs were chosen as the primary pairs, and twenty-two as the exploratory pairs.

Aim 2

Our secondary aim (aim 2) was to correlate cross-sectional dysfunction between LSBN parcellations with specific neuropsychological abnormalities in DLB patients. To accomplish this, we performed a two-stage analysis. First, we compared cognitive test scores between groups to understand which successfully distinguished between the cohorts. When possible, test scores were normed, i.e., converted to a Z- or T-score adjusted for age, sex, and years of education.

Primary Comparisons/A Priori Hypotheses:

- 1) *ADAS Number Cancellation Targets will be lower in DLB patients*
- 2) *Trails B time will be higher in DLB patients*
- 3) *Clock Drawing Tests will be lower in DLB patients*
- 4) *ADAS construction praxis score will be lower in DLB patients*
- 5) *Category Fluency Animals will be lower in AD patients*
- 6) *RAVLT recognition will be lower in AD patients*

The remaining comparisons were exploratory: Trails A time, RAVLT immediate recall, RAVLT delayed recall, Functional Activities Questionnaire (FAQ), Logical Memory Immediate, and Logical Memory Delayed. Digit Span Forward, Digit Span Backward, and Boston Naming Test were either missing or highly incomplete in ADNI controls; therefore, they were described in the DLB cohort only.

In the second part of the Aim 2 analysis, we correlated test scores with FC scores from the primary parcellation group in Aim 1, within diagnosis (DLB, CN, or AD/CI) and compared these correlations across diagnosis group. As above, we prespecified 4 hypotheses to test and consider the remaining correlations to be exploratory. Because of the high volume of statistical tests performed in the exploratory analysis, we used the Holm correction to adjust the p-values in the exploratory correlations only.

Primary/ A Priori Hypotheses:

- 1) *Caudate R / Substantia Nigra R and the Clock Drawing Test will be differently correlated for DLB patients vs other groups.*

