- 2) *Caudate R/ Substantia Nigra R and the ADAS Number Cancellation Targets will be differently correlated for DLB patients vs other groups.*
- 3) *FST R/PH R and the ADAS construction praxis will be differently correlated for DLB patients vs other groups.*
- 4) *FST R / PH R and the Clock Drawing Test will be differently correlated for DLB patients vs other groups.*

With respect to the exploratory correlations, we used a significance threshold of $p < 0.15$, which is an accepted approach for detecting effects in emerging research areas where it's preferable to err on the side of identifying novel effects versus failing to reject a null hypothesis when it is false (Type II error).

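### The updated SAP drops the NPI-Q from the Aim 2 scores without a reason, so no named analysis relates PH-FST, the visual-hallucination pair, to the battery's only neuropsychiatric-symptom scale

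*Combined protocol and SAP*

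**What the plan says.** **Why the pair was chosen.** Protocol section 2.1, Table 2 is titled "Parcellations of Interest for Each DLB Core Symptom". Its visual-hallucinations row reads "Areas PH and FST (Pezzoli et al., 2017". The text before it gives the reasoning for the inferior longitudinal fasciculus: "We suspect that brain regions within this pathway may be compromised in DLB patients with visual hallucinations".

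**What the protocol plans for Aim 2.** Section 8.1 says the correlations are meant "to evaluate the relationship between connectivity strengths and the clinical phenotype of DLB". The scores to be correlated are listed in section 3, ending "Trails A/B, WMS-R Digit Symbol, Clock Drawing, NPI-Q, FAQ, ADAS-Cog 13", and again in Table 4, ending "WMS-R Digit Symbol, Clock Drawing, NPI-Q, FAQ, ADAS-Cog 13". Both lists include the NPI-Q. Table 3 places it in the Visit 2 battery and is the only table entry whose domain is neuropsychiatric symptoms.

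**What the updated SAP plans for Aim 2.** It gives six primary score comparisons, then an exploratory list that begins "The remaining comparisons were exploratory: Trails A time, RAVLT immediate recall, RAVLT delayed recall, Functional Activities Questionnaire (FAQ" and ends with the two Logical Memory scores. Three tests (Digit Span Forward, Digit Span Backward, Boston Naming) are described in DLB only, because the ADNI control data were missing or very incomplete. Four correlation hypotheses are prespecified. Two use FST R/PH R: one is "FST R/PH R and the ADAS construction praxis will be differently correlated", and the other uses the Clock Drawing Test. The NPI-Q is not mentioned anywhere in this text.

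**The concern.** A listed and collected outcome that vanishes between protocol and SAP leaves the reader unable to tell whether it was never analysed, was analysed and not reported, or was set aside for a good reason. The SAP shows that its authors knew how to record such a reason, because they did so for three other tests.

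This omission matters more than most. The primary pairs were selected by core symptom, and the NPI-Q is the only neuropsychiatric-symptom scale in the battery. Without it, PH-FST is related by name only to a constructional praxis score and a drawing test. A result there, in either direction, says little about the symptom that justified studying the pair.

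**Working it through.** The plan gives no figure for this point, so the check is a trace of the scores through the texts, followed by the power that a restored analysis would have.

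**1. Trace of protocol-listed Aim 2 scores with no stated place in the SAP**

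| Score | Section 3 and Table 4 | Table 3 (Visit 2) | Updated SAP |
|---|---|---|---|
| NPI-Q | listed | collected | absent, no reason |
| ANART | listed | collected | absent, no reason |
| WMS-R Digit Symbol | listed | not in the battery | absent, no reason |
| Digit Span F/B, Boston Naming | listed | collected | DLB only, reason given |
| FAQ | listed | collected | exploratory |

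The SAP names 6 primary, 6 exploratory and 3 DLB-only scores. None of these 15 is a neuropsychiatric-symptom measure.

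Two possible explanations can be checked against the text:

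- *Restriction to cognitive performance.* The SAP's first stage speaks of cognitive test scores, and the NPI-Q is not one. But the FAQ, a functional scale in Table 3, is kept.
- *Missing ADNI data.* The documents do not say whether the NPI-Q was incomplete in the ADNI download. If it was, the SAP's own precedent is to keep the test in DLB only. A correlation within DLB uses no ADNI data, and the SAP already correlates within diagnosis.

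**2. Power of an FC by NPI-Q correlation within DLB**

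Inputs: n = 19 (protocol synopsis), assuming all 19 have both measurements. The true correlations r are assumptions; the documents give none.

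Fisher z: SE = 1/√(19 − 3) = 1/√16 = 0.25. Power ≈ Φ(atanh(r)/0.25 − 1.96) at two-sided 0.05.

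- r = 0.3: 0.310/0.25 = 1.238; 1.238 − 1.960 = −0.722; power 24%
- r = 0.4: 0.424/0.25 = 1.695; 1.695 − 1.960 = −0.265; power 40%
- r = 0.5: 0.549/0.25 = 2.197; 2.197 − 1.960 = 0.237; power 59%
- r = 0.6: 0.693/0.25 = 2.773; 2.773 − 1.960 = 0.813; power 79%

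For 80% power, |r| = tanh[(1.960 + 0.842) × 0.25] = tanh(0.700) ≈ 0.60.

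**3. Effect of the Holm family**

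The SAP has eight primary pairs, so one more score adds at most 8 within-DLB correlations. The SAP does not state the family size. As an illustration, assume 8 pairs × 13 scores (the 12 compared scores plus the NPI-Q) = 104 tests. At the SAP's exploratory threshold of 0.15, the smallest p-value must fall below 0.15/104 = 0.00144 (critical z = 3.186). Power for a single correlation at that step is Φ(1.695 − 3.186) ≈ 7% at r = 0.4 and Φ(2.773 − 3.186) ≈ 34% at r = 0.6.

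**The case against.** **The NPI-Q is not forbidden.** Protocol section 8.1 and Table 4 stand in the same combined document and still list it. The SAP's remaining exploratory correlations are not enumerated, and its named score lists serve mainly the between-group comparison. This stands. A reader might infer that PH-FST will never be tested against a symptom measure; the documents support only that no named SAP analysis does so.

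**The SAP's choices fit Aim 2 as worded.** Aim 2 concerns neuropsychological abnormalities. Section 2.1 describes PH as a higher-level visual perception area and FST as integrating detail, motion and form. Correlating the pair with praxis and clock drawing therefore has a basis, and this too stands. The point is the unexplained loss of a listed score, not that those two hypotheses are wrong.

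**The NPI-Q may not measure the mechanism.** The documents describe it only by its neuropsychiatric domain. They specify no hallucination item and no PH-FST by hallucination hypothesis, and a total score would be at best an indirect test. This limits what the restored analysis can claim and how it may be labelled.

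**The problem is not special to this pair.** Table 3 has no dedicated measure of cognitive fluctuations or parkinsonism, so the other symptom-based pairs also lack one. That is true, but the NPI-Q is a symptom scale that the protocol both listed and collected.

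**The test would have little power.** This is correct, as shown above. It argues for an exploratory label and a cautious reading, not for silent omission.

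**Conclusion.** The concern holds as an unreconciled Aim 2 variable list with one consequential gap. The NPI-Q is listed in the protocol, collected at Visit 2, and missing without a reason from every named list in the updated SAP. As a result, no named SAP analysis relates PH-FST to the battery's only neuropsychiatric-symptom scale. ANART and WMS-R Digit Symbol are also unaccounted for; Digit Symbol is not in the Visit 2 battery at all, which may explain its absence but is not stated.

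A reader might go further and argue that, if the PH-FST deficit is confined to patients with hallucinations, the Aim 1 group comparison is diluted by the omission. The documents do not support that. Section 2.1 says only that the pathway may be compromised in such patients and also reports dysfunction of the tract in DLB generally. The share of patients with hallucinations is not given. The Aim 1 test is the same whether or not the NPI-Q is analysed.

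The change is worth making because it is cheap and restores a planned outcome. It is unlikely to be decisive: with 19 complete DLB patients, only correlations of about 0.6 or more reach 80% power, even before Holm adjustment.

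**What to change.** In the updated SAP, Aim 2:

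1. Add the NPI-Q to the Aim 2 scores. Correlate it with the primary-pair FC values, including PH-FST, within DLB, and place these correlations in the exploratory Holm family.
2. Label only this scale-level correlation as protocol-listed.
3. If item scores are stored, add a PH-FST by hallucination-item analysis, labelled post hoc exploratory with the date on which it was added. The SAP is written in the past tense, so the reader needs to know whether results had been seen by then.
4. State the reason for any other protocol-listed score that stays out, at least ANART and WMS-R Digit Symbol.
5. Report the correlations with confidence intervals, and state that a null result at n = 19 is not evidence of no link.

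The cost is a few lines of text and up to eight more tests on data that the protocol already collects. The downside is a slightly larger Holm family, which makes the other exploratory correlations marginally harder to pass, and low power for the added ones.
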